The Medical Monitor must be notified by the clinical institution/site by e-mail or telephone within 24 hours of learning of a Serious Adverse Event. The Medical Monitor may be contacted during business hours for adverse event questions. General study related questions should be directed towards your assigned clinical research associate.

[figure not shown]
[figure not shown]
The Medical Monitoring Plan is maintained as a separate document and included in the Trial Master File.

Clinical Study Protocol

Johnson & Johnson Vision Care, Inc.

AUTHORIZED SIGNATURES

The signatures below constitutes the approval of this protocol and the attachments and provide the necessary assurances that this trial will be conducted according to all stipulations of the protocol, including all statements regarding confidentiality, and according to local legal and regulatory requirements and applicable U.S. federal regulations³, ISO 14155:2020¹, and the Declaration of Helsinki².

Author		21st August 2022
		DATE
Study Responsible Clinician	See Electronic Signature Page	
		DATE
Clinical Operations Manager	See Electronic Signature Page	
		DATE
Biostatistician	See Electronic Signature Page	
		DATE
Data Management	See Electronic Signature Page	
		DATE
Medical Safety Officer	See Electronic Signature Report	
		DATE
Approver	See Electronic Signature Page	
		DATE

Clinical Study Protocol
Johnson & Johnson Vision Care, Inc.

CHANGE HISTORY

Version	Originator	Description of Change(s) and Section Number(s) Affected	Justification for Change	Date
1.0		Original Protocol	N/A	19 Jul 2022
2.0		Dropped one of the Control lenses and reduced to a 2x2 crossover study	Business decision	19 Aug 2022

Clinical Study Protocol

Johnson & Johnson Vision Care, Inc.

SYNOPSIS

Protocol Title	Clinical performance of two daily disposable silicone hydrogel contact lenses ()
Sponsor	JJVC, [name]
Clinical Phase	Clinical trial phase: Post Market Development phase: Phase 4
Trial Registration	This study will be registered on ClinicalTrials.gov based on the following: although the study is a pilot study of a new type of clinical measurement, it involves the use of marketed contact lenses and it is being conducted in the United Kingdom.
Test Article(s)	Investigational Products: Acuvue® Oasys MAX 1-Day daily disposable contact lenses Dailies Total 1 daily disposable contact lenses
Wear and Replacement Schedules	Wear Schedule: daily wear Replacement Schedule: daily disposable
Objectives	Assess lens fit acceptance of the Acuvue® Oasys MAX 1-day contact lens and the Dailies Total 1 daily disposable contact lens.
Study Endpoints	Primary Endpoint(s): Lens fit acceptance. Other Exploratory Endpoint(s): Slit lamp findings, tear film stability, patient reported outcomes.
Study Design	This is a subject-masked, randomized, bilateral, 2x2 crossover dispensing clinical investigation. Each subject will be fitted bilaterally with one test article in each of the two periods. Subjects will wear a pair of Acuvue® Oasys MAX 1-day contact lenses for 7 to 14 days and a pair of Dailies Total 1 contact lenses for 7 to 14 days in a randomized order. There will be a total of 3 visits: Visit 1: Screening, baseline evaluation, and lens fit #1. Visit 2: Clinical evaluation, and lens fit #2. Visit 3: Clinical evaluation, and final evaluation. See the flow chart at the end of the synopsis table for the schematic of the study visits and procedures of main observations (Figure 1).
Sample Size	Up to 16 subjects will be enrolled, with recruitment ceasing once 10 subjects have successfully completed the study.
Study Duration	September 2022 to November 2022
Anticipated Study Population	Current daily disposable contact lens wearers aged 18 to 40 with normal, healthy eyes.

Clinical Study Protocol

Johnson & Johnson Vision Care, Inc.


Eligibility Criteria - Inclusion
	
Potential subjects must satisfy all of the following criteria to be enrolled in the study:
 
Inclusion Criteria following Screening:
 
 1. The subject must read, understand, and sign the STATEMENT OF INFORMED CONSENT and receive a fully executed copy of the form. 2. Appear able and willing to adhere to the instructions set forth in this clinical protocol. 3. Between 18 and 40 (inclusive) years of age at the time of screening. 4. They agree not to participate in other clinical research while enrolled on this study. 5. They have worn the same brand of soft daily disposable silicone hydrogel contact lenses at least eight hours per day for at least four days per week over the past 4 weeks. 6. They own a wearable pair of spectacles if needed for distance vision correction (by self-report). 
Inclusion Criteria at Baseline Evaluation:
 
 7. They can attain a best-corrected logMAR distance visual acuity of at least 0.20 in each eye. 8. They have spherical contact lens prescription in the range -1.00 to -6.00 DS (based on the calculated ocular refraction). 9. They have up to maximum of 1.00 DC of refractive astigmatism (based on the calculated ocular refraction).

Eligibility Criteria – Exclusion
	
Potential subjects who meet any of the following criteria will be excluded from participating in the study:
 
Exclusion Criteria following Screening:
 
 1. Currently pregnant or lactating. 2. Any systemic disease (e.g., Sjögren’s Syndrome), allergies, infectious disease (e.g., hepatitis, tuberculosis), contagious immunosuppressive diseases (e.g., HIV), autoimmune disease (e.g. rheumatoid arthritis), or other diseases, by self-report, which are known to interfere with contact lens wear and/or participation in the study or may pose a risk to study personnel. 3. They have an ocular disorder, which would normally contraindicate contact lens wear. 4. They have had cataract surgery. 5. They have had corneal refractive surgery. 6. They are using any topical medications such as eye drops or ointments.

Clinical Study Protocol

Johnson & Johnson Vision Care, Inc.

	
7. Any known hypersensitivity or allergic reaction to sodium fluorescein.
 
8. Use of systemic medications (e.g., chronic steroid use) that are known to interfere with contact lens wear. See section 9.1 for additional details regarding excluded systemic medications.
 
9. Participation in any contact lens or lens care product clinical trial within 2 weeks prior to study enrollment.
 
10. Employee or immediate family member of an employee of clinical site (e.g., Investigator, Coordinator, Technician).
 
Exclusion Criteria at Baseline Evaluation:
 
11. They have any corneal distortion resulting from previous hard or rigid lens wear or have keratoconus.
 
12. Any Efron Grade 3 or greater slit lamp findings (e.g., edema, corneal neovascularization, corneal staining, tarsal abnormalities, conjunctival injection).
 
13. They have a pre-corneal tear film break-up time less than five seconds when evaluated on the Digital Eye Strain Manchester Device (DESMD) tear film imaging system.

Disallowed Medications / Interventions
	
No ocular topical medications (including comfort drops) from 24 hours prior to study visits or during the wear of any study lenses.
 
No systemic medications that in the view of the investigator may affect the ocular surface or contact lens wear from 24 hours prior to study visits.
 
See section 9.1 for details regarding disallowed systemic medications.

Measurements and Procedures
	
Assessment of acceptable fit rate. Assessment of tear film stability using the DESMD tear film analysis system, slit lamp biomicroscopy, logMAR visual acuity assessment.

Microbiology or Other Laboratory Testing
	
None.

Study Termination
	
The occurrence of one or more Unanticipated Adverse Device Effect (UADE), or any SAE where relationship to study agent cannot be ruled out, will result in stopping further dispensing investigational product. In the event of a UADE or SAE, the Sponsor Medical Monitor may unmask the treatment regimen of subject(s) and may discuss this with the Principal Investigator before any further subjects are enrolled.

Ancillary Supplies/ Study-Specific Materials
	
Any Sponsor-approved saline pods and fluorescein strips

Clinical Study Protocol
Johnson & Johnson Vision Care, Inc.

Principal Investigator(s) and Study Institution(s)/Site(s)	A full list of Principal Investigators, clinical sites, and institutions is kept separately from the Study Protocol and is included in the study Trial Master File.
--	---

Clinical Study Protocol

Johnson & Johnson Vision Care, Inc.

Figure 1: Study Flowchart

Clinical Study Protocol

Johnson & Johnson Vision Care, Inc.

COMMONLY USED ABBREVIATIONS AND DEFINITIONS OF TERMS

ADD	Plus Power Required For Near Use
ADE	Adverse Device Effect
AE	Adverse Event/Adverse Experience
BCVA	Best Corrected Visual Acuity
BSCVA	Best Spectacle Corrected Visual Acuity
CFR	Code of Federal Regulations
COAS	Complete Ophthalmic Analysis System
COM	Clinical Operations Manager
CRA	Clinical Research Associate
CRF	Case Report Form
CRO	Contract Research Organization
CT	Center Thickness
	
CVS	Computer Vision Syndrome
D	Diopter
DES	Digital Eye Strain
DESMD	Digital Eye Strain Manchester Device
DMC	Data Monitoring Committee
eCRF	Electronic Case Report Form
EDC	Electronic Data Capture
ETDRS	Early Treatment Diabetic Retinopathy Study
FDA	Food and Drug Administration
GCP	Good Clinical Practice
HIPAA	Health Insurance Portability and Accountability Act
IB	Investigator's Brochure
ICF	Informed Consent Form
ICH	International Conference on Harmonization
IDE	Investigational Device Exemption
IEC	Independent Ethics Committee
IRB	Institutional Review Board
ISO	International Organization for Standardization
ITT	Intent-to-Treat
JJVC	Johnson & Johnson Vision Care, Inc.
LC	Limbus Center
LogMAR	Logarithm of Minimal Angle of Resolution
MOP	Manual of Procedures
NIH	National Institutes of Health
OD	Right Eye
OHRP	Office for Human Research Protections
OHSR	Office for Human Subjects Research
OS	Left Eye
OU	Both Eyes
PD	Protocol Deviation
PHI	Protected Health Information

Clinical Study Protocol

Johnson & Johnson Vision Care, Inc.

PI	Principal Investigator
PIG	Patient Instruction Guide
PQC	Product Quality Complaint
PRO	Patient Reported Outcome
QA	Quality Assurance
QC	Quality Control
SAE	Serious Adverse Event/Serious Adverse Experience
SAP	Statistical Analysis Plan
SAS	Statistical Analysis System
SD	Standard Deviation
SOP	Standard Operating Procedure
UADE	Unanticipated Adverse Device Effect
USADE	Unanticipated Serious Adverse Device Effect
VA	Visual Acuity
DES	Digital Eye Strain

1. INTRODUCTION AND BACKGROUND

Acuvue[®] Oasys MAX 1-Day is a new contact lens technology, which has been developed to offer improved clinical performance over existing contact lens designs. This study seeks to assess the clinical performance of this new lens type in comparison with the Dailies Total 1 contact lens. This comparison will focus on acceptable fit rates, with other clinical metrics assessed including slit lamp biomicroscopy findings and tear film stability.

1.1. Name and Descriptions of Investigational Products

This clinical study will evaluate two soft contact lens types: Acuvue[®] Oasys MAX 1-Day (JJVC) daily disposable contact lenses, and Dailies Total 1 (Alcon) daily disposable contact lenses. These lens types are CE marked. Further details about the test articles are found in section 6 of this protocol.

1.2. Intended Use of Investigational Products

The intended use of the CE marked contact lens products is for correcting myopia. During the study, each study lens type will be worn bilaterally in daily wear, daily disposable modality for at least 8 hours per day for a period of 7 to 14 days. No more than two days of missed lens wear are allowed on the days between fitting and follow-up.

Subjects will wear Acuvue[®] Oasys MAX 1-day contact lenses for 7 to 14 days and Dailies Total 1 contact lenses for 7 to 14 days in a randomized order.

1.3. Summary of Findings from Nonclinical Studies

Not Applicable – Marketed product only.

Clinical Study Protocol

Johnson & Johnson Vision Care, Inc.

1.4. Summary of Known Risks and Benefits to Human Subjects

This study will use approved marketed products. The following risks/adverse events can be associated with the use of any marketed contact lens:

- Discomfort, pain, watering or unusual secretions of the eyes
- Redness of the eyes
- Reduced vision and sensitivity to light
- In very rare instances corneal infection, scarring or permanent loss of vision may occur

The key invasive procedures in this work and their associated risks are outlined below:

Staining of the ocular surface with sodium fluorescein

- Some temporary discomfort on application
- Very rarely, anaphylaxis with topical application

There is no direct benefit to the subjects enrolled other than being able to try lens types that they have not had the opportunity to try before. The information obtained from this study may aid in the development of improved contact lenses in the future.

In order to minimize the likelihood of adverse events, subjects will undergo an ocular examination before and after the clinical investigations. Subjects will also be trained on what to do if they develop ocular discomfort, redness, or reduced vision and what to do if they need to be seen outside of the Eurolens Research clinic opening hours.

For the most comprehensive risk and benefit information regarding Acuvue[®] Oasys MAX 1-Day, and Dailies Total 1 refer to the latest version of the package insert of the marketed products (Appendix C).

1.5. Relevant Literature References and Prior Clinical Data Relevant to Proposed Clinical Study

Acuvue[®] Oasys MAX 1-Day, and Dailies Total 1 are CE marked/approved and marketed products (APPENDIX C: PACKAGE INSERT (APPROVED PRODUCT)).

2. STUDY OBJECTIVES, ENDPOINTS AND HYPOTHESES

2.1. Objectives

Assess lens fit acceptance of the Acuvue[®] Oasys MAX 1-day contact lens and the Dailies Total 1 daily disposable contact lens.

2.2. Endpoints

Primary Endpoint(s):

Lens Fit Acceptance

Lens fit acceptance will be assessed at dispensing and follow-up visits for each subject eye. Acceptable fit is a binary response where Y=1 if lens fit is deemed acceptable by the

Clinical Study Protocol

Johnson & Johnson Vision Care, Inc.

investigator and $Y=0$ otherwise. An unacceptable fit is deemed by one or more of the following criteria:

- limbal exposure at primary gaze or with extreme eye movement
- edge lift
- excessive movement with blink in primary gaze
- insufficient movement with blink in upgaze
- insufficient movement in push-up test

Other Observations:

Slit Lamp Findings

The slit lamp findings (biomicroscopy) will be assessed for each subject eye across all study visits (including scheduled and unscheduled visits). The Efron grading scale will be used to quantify the slit lamp observations.

Tear Film Stability

Tear film stability (tear film surface quality) will be assessed in the left eye (OS) only. The Digital Eye Strain Manchester Device (DESMD) system uses an off-axis infrared ring projection illumination system to produce a reflected mire pattern on the tear film surface. Image processing will then be used to assess tear film surface quality and calculate the tear film break-up time. Tear film break-up time will be assessed three times, with a five-minute break between measurements.

Patient Reported Outcomes

Subjective impressions of the study lenses will be assessed using the CLDEQ-8 questionnaire, and two additional questions regarding the subject's opinion of the lenses.

CLDEQ-8 is a validated patient-reported outcome measure assessing patient-experience of symptoms relating to contact lens dryness.⁵ The sum of the item scores of CLDEQ-8 ranges from 0 to 37 where higher scores indicate more dryness with respect to contact lens wear.

2.3. Hypotheses

Primary Hypothesis:

Lens Fit Acceptance

Acceptable fit rate will be calculated by visit for each lens type. No statistical hypotheses will be tested.

3. TARGETED STUDY POPULATION

3.1. General Characteristics

The study population will be healthy contact lens wearers aged 18-40 years of age from a single site in the United Kingdom (UK).

Clinical Study Protocol

Johnson & Johnson Vision Care, Inc.

3.2. Inclusion Criteria

Potential subjects must satisfy all of the following criteria to be enrolled in the study:

Inclusion Criteria following Screening:

1. The subject must read, understand, and sign the STATEMENT OF INFORMED CONSENT and receive a fully executed copy of the form.
2. Appear able and willing to adhere to the instructions set forth in this clinical protocol.
3. Between 18 and 40 (inclusive) years of age at the time of screening.
4. They agree not to participate in other clinical research while enrolled on this study.
5. They have worn the same brand of soft daily disposable silicone hydrogel contact lenses at least eight hours per day for at least four days per week over the past 4 weeks.
6. They own a wearable pair of spectacles if needed for distance vision correction (by self-report).

Inclusion Criteria at Baseline Evaluation:

7. They can attain a best-corrected logMAR distance visual acuity of at least 0.20 in each eye.
8. They have spherical contact lens prescription in the range -1.00 to -6.00 DS (based on the calculated ocular refraction).
9. They have up to maximum of 1.00 DC of refractive astigmatism (based on the calculated ocular refraction).

3.3. Exclusion Criteria

Potential subjects who meet any of the following criteria will be excluded from participating in the study:

Exclusion Criteria following Screening:

1. Currently pregnant or lactating.
2. Any systemic disease (e.g., Sjögren's Syndrome), allergies, infectious disease (e.g., hepatitis, tuberculosis), contagious immunosuppressive diseases (e.g., HIV), autoimmune disease (e.g., rheumatoid arthritis), or other diseases, by self-report, which are known to interfere with contact lens wear and/or participation in the study or may pose a risk to study personnel.
3. They have an ocular disorder which would normally contraindicate contact lens wear.
4. They have had cataract surgery.
5. They have had corneal refractive surgery.
6. They are using any topical medications such as eye drops or ointments.
7. Any known hypersensitivity or allergic reaction to sodium fluorescein.
8. Use of systemic medications (e.g., chronic steroid use) that are known to interfere with contact lens wear. See section 9.1 for additional details regarding excluded systemic medications.

Clinical Study Protocol

Johnson & Johnson Vision Care, Inc.

9. Participation in any contact lens or lens care product clinical trial within 2 weeks prior to study enrollment.
10. Employee or immediate family member of an employee of clinical site (e.g., Investigator, Coordinator, Technician).

Exclusion Criteria at Baseline Evaluation:

11. They have any corneal distortion resulting from previous hard or rigid lens wear or have keratoconus.
12. Any Efron Grade 3 or greater slit lamp findings (e.g., edema, corneal neovascularization, corneal staining, tarsal abnormalities, conjunctival injection),
13. They have a pre-corneal tear film break-up time less than five seconds when evaluated on the DESMD tear film imaging system.

3.4. Enrollment Strategy

Study subjects will be recruited from the Eurolens Research (The University of Manchester) subject database and/or utilizing Independent Ethics Committee (IEC) or Institutional Review Board (IRB) approved materials.

4. STUDY DESIGN AND RATIONALE

4.1. Description of Study Design

This is a subject-masked, randomized, bilateral, 2x2 crossover dispensing clinical investigation.

Visit 1 – Screening/Baseline/Lens Fitting #1

Up to 16 subjects will be enrolled, with recruitment ceasing once 10 subjects have successfully completed the study.

At study Visit 1, subjects will be consented and screened for inclusion/exclusion criteria. If a subject is found to meet all eligibility criteria, they will be fitted with the first study lens based on the randomization scheme; otherwise, the subject will be discontinued from the study. The subject will then be dispensed with the study lenses to wear on a daily disposable basis for a period of 7 to 14 days.

Visit 2 - Assessment 1/Lens Fitting #2

Subjects will attend after having worn the study lenses for at least 6 hours. At this visit, DESMD tear film stability will be assessed during a period of extended eye opening (three times on the left eye only, with a 5-minute break between measurements). The second lens type will then be fitted. The subject will then be dispensed with the study lenses to wear on a daily disposable basis for a period of 7 to 14 days.

Clinical Study Protocol

Johnson & Johnson Vision Care, Inc.

Visit 3 – Assessment 2

Subjects will attend after having worn the study lenses for at least 6 hours. At this visit, DESMD tear film stability will be assessed during a period of extended eye opening (three times on the left eye only, with a 5-minute break between measurements). Subjects will then be exited from the study.

4.2. Study Design Rationale

The purpose of this study is to evaluate the performance of Acuvue® Oasys MAX 1-Day daily disposable contact lenses compared to Dailies Total 1 daily disposable contact lenses. A 2×2 crossover design is used. Crossover designs are a well-established study design in which subjects are exposed to multiple treatments during different time periods. This design is cost effective and more efficient since it eliminates part of the inter-subject variability from the treatment comparisons. Subjects will be randomized into the two lens wear sequences. Randomization eliminates the selection bias and balances both the known and unknown confounding factors that may affect the study outcomes.

4.3. Enrollment Target and Study Duration

Up to 16 subjects will be enrolled, with a target of 10 subjects successfully completing the study.

The study will last approximately 3 months. Once the informed consent has been signed the subject will be considered enrolled. Subjects who are discontinued prior to the final evaluation will be replaced. Study recruitment will cease once 10 subjects have completed all study visits.

5. TEST ARTICLE ALLOCATION AND MASKING

Subjects will wear Acuvue® Oasys MAX 1-day contact lenses for 7 to 14 days and Dailies Total 1 contact lenses for 7 to 14 days in a randomized order.

5.1. Test Article Allocation

Subjects will wear Acuvue® Oasys MAX and Dailies Total 1 sequentially in a random order. Subjects will be randomly assigned to one of the two lens wear sequences: Acuvue® Oasys MAX 1-Day/Dailies Total 1 or Dailies Total 1/Acuvue® Oasys MAX 1-Day.

The randomization scheme will be provided by the study responsible biostatistician and will be generated using the Statistical Analysis System (SAS) software Version 9.4 or higher (SAS Institute, Cary, NC).⁴

The clinical site will follow the randomization scheme provided and will complete enrollment according to the randomization list and will not pre-select or assign subjects.

Randomization will be performed at visit 1. The following must have occurred prior to randomization:

Clinical Study Protocol

Johnson & Johnson Vision Care, Inc.

- Informed consent must have been obtained.
- The subject must have met all eligibility criteria.
- The subject's screening and baseline information must have been collected.

5.2. Masking

This is a single masked study where subjects are masked to the identity of the study contact lenses during the study. The investigators and technical personnel involved in the data collection may be aware of the study lenses based on a slight difference in lens color (the Test lens will be slightly more turquoise in color than the Control lens).

5.3. Procedures for Maintaining and Breaking the Masking

The identity of the investigational products will be masked by over labelling the contact lens blister packs with a label containing the study number and expiration date.

Under normal circumstances, the mask should not be broken until all subjects have completed the study and the database is finalized. Otherwise, the mask should be broken only if specific emergency treatment/course of action would be dictated by knowing the treatment status of the subject. In such cases, the Investigator may, in an emergency, contact the medical monitor. In the event the mask is broken, the Sponsor must be informed as soon as possible. The date, time, and reason for the unmasking must be documented in the subject record.

Subjects who have had their treatment assignment unmasked are expected to return for all remaining scheduled evaluations. Subjects who are discontinued will be replaced.

When conducting the visit, the following steps should be followed to maintain randomization codes:

1. Investigator or designee (documented on the Delegation Log) will consult randomization scheme to obtain the test sequence assignment for that subject prior to DESMD system assessment.
2. Investigator or designee will record the subject's number on the appropriate line of the randomization scheme.
3. Investigator or designee will pull the appropriate test articles from the study supply. All test articles that are opened, whether dispensed (placed/fit on eye or dispensed outside the clinical site) or not, must be recorded on the Test Article Accountability Log in the "Dispensed" section.

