7. STUDY EVALUATIONS

7.1. Time and Event Schedule

Table 3: Time and Events

Visit Information	Visit 1 Screening, Baseline, Treatment 1 Lens Fitting	Visit 2 Treatment 1 Follow-up/ Treatment 2 Lens Fitting	Visit 3 Treatment 2 Follow-up
Time Point	N/A	7 to 14 days from Visit 1	7 to 14 days from Visit 2
Estimated Visit Duration	2 hours	2 hours	1.5 hours
Statement of Informed Consent	x		
Demographics	x		
Medical History/Concomitant Medications	x	x	x
Habitual Contact Lens Information	x		
Inclusion/Exclusion Criteria	x		
Adverse event review	x	x	x
Subjective Sphero-Cylindrical Refraction	x		
LogMAR Visual Acuity	x	x	x
Slit Lamp Biomicroscopy	x	x	x
Corneal topography	x		
Lens application	x	x	
Over Refraction (with lenses)	x	x	
Lens Fit Assessment	x	x	x
DESMD tear film assessment	x	x	x
Dispense study lenses	x	x	
Exit LogMAR Visual acuity	x	x	x
Final Evaluation			x

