1.8	Subjective Sphero-cylindrical Refraction	Subjective sphero-cylindrical refraction will be performed on both eyes.	[REDACTED]
1.9	Entrance LogMAR Visual Acuity	Distance high contrast visual acuity will be measured OD, OS and OU with the subjective refraction in place.	Appendix E: Eurolens Research SOP # 12A
1.10	Slit Lamp Biomicroscopy	
Grades will be scored to the nearest 0.1 in the best judgment of the investigator using Efron Grading Scales.
 
If any slit lamp findings are Efron Grade 3 or greater (e.g., corneal edema, corneal neovascularization, tarsal abnormalities, conjunctival injection), the subject may not continue at this time, but may return up to one additional time to determine eligibility. If discontinued a final examination must be completed.
 
If the clearance of the fluorescein needs to be expedited, preservative-free rewetting drops or saline may be instilled.
	Appendix F: Eurolens Research SOP # 13
1.11	Corneal topography	Corneal topography using the Medmont topographer will be carried out on each eye. Simulated K readings (mm) will be documented.	Eurolens Research SOP # 16

Clinical Study Protocol

Johnson & Johnson Vision Care, Inc.

Visit 1: Baseline			
Step	Procedure	Details	
1.12	DESMD environmental conditions	Record the room temperature and humidity	Appendix G
1.13	DESMD system tear film measurements (extended eye opening) without study contact lenses	
Pre-corneal tear film stability will be assessed using the DESMD system during a period of extended eye opening. Subjects will be asked to keep their left eye open for as long as they can (maximum of 30 seconds), with the subject's right eye occluded during the test. Tear film stability will be assessed on three occasions with a 5-minute break between measurements.
 
If the median pre-corneal tear film break-up time is less than 5 seconds, the subject is not eligible to continue in the study.
	Appendix G
1.14	Eligibility after Baseline	
All responses to Inclusion Criteria questions must be answered "yes" and all responses to Exclusion Criteria questions must be answered "no" for the subject to be considered eligible.
 
If subject is deemed to be ineligible after baseline, proceed to Final Evaluation and complete all forms.
	
1.15	Randomization	Subjects will be randomized to follow one of two possible lens wear sequences.	

Visit 1: Treatment 1 Lens Fitting			
Step	Procedure	Details	

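### Do the loose timing of the sequence look-up in Section 5.3 and the misnumbered repeat range in step 1.19 put randomization out of order?

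*Combined protocol and SAP*

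**What the plan says.** Section 5.3 introduces three site steps with "When conducting the visit, the following steps should be followed to maintain randomization codes". In step 1 staff "consult randomization scheme to obtain the test sequence assignment for that subject prior to DESMD system assessment"; in step 2 they "record the subject's number on the appropriate line of the randomization scheme"; in step 3 they take the lenses from stock. No visit number is attached to any of these.

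Section 5.1 fixes the timing of allocation: "Randomization will be performed at visit 1. The following must have occurred prior to randomization". The list that follows covers consent, the collection of screening and baseline information, and eligibility: "The subject must have met all eligibility criteria".

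Table 3 in Section 7.1 marks "DESMD tear film assessment" at Visits 1, 2 and 3. The Visit 1 test serves exclusion criterion 13 in Section 3.3: "They have a pre-corneal tear film break-up time less than five seconds when evaluated on the DESMD tear film imaging system". Step 1.13 in Section 7.2 applies it: "If the median pre-corneal tear film break-up time is less than 5 seconds, the subject is not eligible to continue in the study". Step 1.14 then confirms eligibility, step 1.15 is Randomization, and step 1.16 is application of the first lens.

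Step 1.19 allows up to two changes of lens power and sends staff back through steps 1.15 to 1.18. The Visit 2 counterpart, step 2.16, sends them back through 2.13 to 2.16.

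**The concern.** Randomization happens at Visit 1, and a DESMD test also takes place at Visit 1. The natural first reading of Section 5.3 is therefore that the sequence is looked up, and the subject entered on the list, before that test. The test is both baseline information and an eligibility criterion, so on this reading Section 5.3 reverses the order that Section 5.1 requires. A subject could take a list line and then be excluded. Staff could also know the next sequence while the DESMD eligibility decision was still open.

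The repeat range in step 1.19 adds to the unease. Taken literally, it returns a subject to Randomization after a power change, and it ends one step short of the over-refraction that the Visit 2 range includes.

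**Working it through.** No sample size, power or error rate is involved. The check is of step order, followed by a bound on the consequence.

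**1. Section 5.3 read at each visit**

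| Visit | DESMD step | Status of the subject at that step | Conflict with 5.1? |
|---|---|---|---|
| 1 | 1.13, no study lens on the eye | not yet confirmed eligible (1.14) or randomized (1.15) | yes |
| 2 | 2.10, first study lens on | randomized at 1.15 | no |
| 3 | 3.10, second study lens on | randomized at 1.15 | no |

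A look-up at step 1.15 precedes every DESMD test made on a study lens. Section 4.1, which describes the visits in outline, mentions DESMD only at Visits 2 and 3. The conflict is therefore conditional on the Visit 1 reading.

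**2. What governs the order at Visit 1.** Section 5.1 lists the preconditions, and steps 1.13, 1.14 and 1.15 put them in numbered sequence. Steps 1.16 and 2.13, where the assignment is used, both refer staff to the randomization table. Section 5.3 concerns masking and does not claim to override any of this.

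**3. The repeat range**

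| Procedure | Visit 2 | Visit 1 |
|---|---|---|
| Lens application | 2.13 | 1.16 |
| Settling | 2.14 | 1.17 |
| Fit assessment | 2.15 | 1.18 |
| Acuity and over-refraction | 2.16 | 1.19 |

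By analogy with Visit 2 the range should read 1.16 to 1.19; it is printed as 1.15 to 1.18. The lower end is plainly a numbering slip. The upper end does no harm. The instruction sits inside step 1.19, so finishing 1.18 leads straight back to 1.19, where the over-refraction is done. A second power change, also allowed there, presupposes that return. Acuity with the study lenses on is measured again at 1.20, and the dispensing minimum is applied at 1.21.

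**4. Size of the consequence if Section 5.3 were applied at Visit 1**

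- Ceiling on list lines taken by subjects who then fail step 1.13, given that 10 complete: 16 − 10 = 6. This counts non-completers from every cause, so the number lies between 0 and 6.
- The documents give no DESMD failure rate p, so I assume 5%, 10% and 20%. Recruitment stops at 10 completers (Section 4.3). If DESMD failure is the only loss, and the cap of 16 is ignored, expected failures are 10p/(1 − p):
  - p = 0.05: 10 × 0.05/0.95 = 0.5
  - p = 0.10: 10 × 0.10/0.90 = 1.1
  - p = 0.20: 10 × 0.20/0.80 = 2.5
- If all 16 were tested because of other losses, the expectation would be 16p: 0.8, 1.6 and 3.2.

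**5. Effect on the analysis.** Section 14.5 calculates the fit rate in the safety population, which Section 14.3 limits to subjects given a test article. A subject who fails at 1.13 never reaches lens application at 1.16. Such a subject might count as randomized and so fall in the intent-to-treat set, but Section 14 assigns no analysis to that set. Section 14.4 makes all planned analysis descriptive. Subjects added to or removed from the primary analysis: 0.

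**The case for a change.** The best case for a correction is that the Visit 1 reading is not strained. Entering the subject on a list line and pulling lenses describe first allocation, which happens at Visit 1. Doing this for the first time at Visit 2 would be too late, because step 1.16 already relies on the assignment. At Visit 3 no new lens is applied. So no single visit suits all three steps of Section 5.3 together with its DESMD reference. Section 10 prohibits waivers and requires deviations to be reported within 24 hours, so contradictory instructions could leave staff unsure what counts as compliant. The rewording would be short.

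Much of this stands. The phrase is loose, and step 1.19 contains a real misnumbering. It does not follow that anyone would be misled. A reader who took Section 5.3 at Visit 1 would be stopped by the explicit preconditions in Section 5.1 and by the numbered steps that staff follow during the visit.

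The worry about knowing the next sequence too early would not be cured by rewording. The site holds the list under either wording, so the change would create no allocation concealment. In this crossover, moreover, both sequences contain both lenses, so early knowledge bears on order alone. The plan also accepts that lines are lost after randomization, since Section 4.3 replaces subjects who discontinue. Finally, the cost is small but not nil, because Section 18.3 sends protocol revisions to the ethics committee where appropriate.

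**Conclusion.** No change follows. These are two clerical slips. One is a timing phrase that conflicts with Section 5.1 only if read at Visit 1; the other is a step range whose lower end is one too low. The correct order is stated in Section 5.1 and again in steps 1.13 to 1.15, and no one would read a power change as grounds for a second randomization. The over-refraction is not lost, because the repeat instruction leads back into the step that contains it.

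On the unfavourable reading, between 0 and 6 list lines could be spent on subjects who then fail the DESMD test, provided 10 subjects complete. The expected number is about 0.5 to 2.5 at assumed failure rates of 5% to 20% if there are no other losses, and at most 0.8 to 3.2 if all 16 are tested. These rates are assumptions, and the conclusion does not depend on them: the primary analysis gains or loses 0 subjects whatever the rate. This rests on the safety population remaining the primary set, on all planned analysis remaining descriptive, and on staff following the numbered procedures in Section 7.2.
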